The overall goal of this project is to investigate the mechanisms of optimized tDCS via two important markers of chronic pain, conditioning pain modulation (CPM) and slow temporal summation (STS). In addition, the results of this study will represent a significant step toward developing a novel low-cost therapy for FM and validating a therapeutic novel target.

Sponsors

This study is funded by NIH-NCCIH (1 R01 AT009491-01A1).

II. SPECIFIC AIMS

This trial aims at understanding the mechanisms of optimized tDCS (16 tDCS sessions combined with exercise) on pain control. Optimized tDCS can lead to stronger engagement of the endogenous pain regulatory system that will ultimately lead to increased pain relief in patients with FM. Therefore, we designed a 2x2 factorial mechanistic trial [tDCS (active and sham) and aerobic exercise (active and control)] to test the following aims:

Aim 1 (primary outcome): Evaluate the effects of 4 weeks of tDCS coupled with exercise on the endogenous pain regulatory system assessed by CPM and central sensitization as assessed by TSPS, and compared to either intervention alone and to no intervention. *We hypothesize that tDCS coupled with exercise will result in restoration of pain endogenous regulatory system as indexed by greater decrease in SPS and increase in CPM responses. We also hypothesize to observe differences between groups as exercises may have a larger effect on the insula and somatosensory cortex (which is indexed by SPS) while tDCS seems to have a greater effect on prefrontal and*

cingulate cortex (which is indexed by CPM). Thus, these markers will be important to understand to what extend the nodes of pain matrix may be more involved in pain relief and whether the effects of tDCS and exercises are mainly mediated by an increase in inhibition (increase of CPM) or a decrease of excitation (decrease of TSPS).

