Aim 2: Determine the effect of these interventions on cortical markers of inhibitory control that are also affected in FM, such as intracortical inhibition as assessed by transcranial magnetic stimulation (TMS) and changes in thalamocortical dysrhythmia as assessed by EEG. *We hypothesize that active tDCS combined with exercise will result in greater increases in intracortical inhibition as measured by the short intracortical inhibition (SICI). These increases will be associated with greater reduction of pain when compared to either intervention alone. We also hypothesize that tDCS combined with exercise will induce a greater decrease in theta power than any intervention alone, as well as to the control group. Therefore, we hypothesize that decreases in theta EEG band power could be used as a marker of the normalization of the thalamic dysrhythmia normalization.*

Aim 3: Assess the number of sessions needed to induce significant changes in markers of endogenous pain inhibitory system and central sensitization (CPM and TSPS) and cortical changes (as indexed by paired pulse TMS and EEG). *We hypothesize that the group receiving the top-down and bottom-up strategies (tDCS and AE) will have a greater number of subjects with target engagement (change of at least 30% as compared to baseline) of pain and cortical marker.*

Sub-aim 3: Assess whether engagement of the two main targets tested in this study – TSPS and CPM – are associated with the secondary clinical outcomes (i.e., changes in pain outcomes: Brief Pain Inventory, Revised Fibromyalgia Impact Questionnaire). *We hypothesize that changes in TSPS and CPM will be correlated with these pain outcomes. We also hypothesize to find a correlation between baseline values of TSPS and CPM and pain relief immediately after the intervention.* This result will be important as to assess the suitability of such markers as potential treatment response predictors.

[figure not shown]
III MEDICAL MONITOR

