Sample Size Calculation: This study's original sample size calculation was based on an expected effect size of 0.78, with 85% statistical power and a significance level of 0.05. However, after 6 years of the original sample size calculation (it was done in 2017 upon grant submission, see appendix 2), we have observed in our recent study in collaboration with other colleagues and recent meta-analyses effect sizes ranging from 0.9 to 1.26, which are larger than we initially anticipated. Considering this new information, we re-estimated the sample size to ensure we do not expose subjects to the burden of participating in a study that involves a placebo arm. Also, this would make the study feasible to be completed in the 5-year period of this grant, given our recruitment was significantly affected by the COVID pandemic, especially in the years 2020 and 2021. We have recalculated the sample size using the smallest reported effect size (0.90) using the t-test calculation for the difference between two independent means (to test for the main hypothesis) – this is the same method used in the original sample size calculation; and determined that we need a total of 116 participants (29 in each group) to achieve 85% power (as planned before). We assumed a type I error of 5% (alpha), and a type 2 error of 15% (beta). We also made this calculation considering the same parameters used in the original sample size calculation, such as dropout rates of 20%. The sensitivity analysis for the sample size calculation is summarized in the table below.

[figure not shown]
Therefore, we reduced the sample size from 148 to 116 participants, which will maintain the same planned statistical power (85%). This revised sample size will allow us to detect the more precise effect sizes currently reported in the literature and will also make the study feasible to be completed on time, given the large impact of the COVID pandemic on our study.

[figure not shown]
Planned Analysis:

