The primary analysis: All the analyses will be performed as intention-to-treat in which all subjects undergoing randomization who receive at least one intervention session (randomization will take place immediately before the first intervention) will be included. We will conduct sensitivity analyses and test different models of handling missing data (LOFC and MI). The change in the primary efficacy endpoint, CPM (and also TSPS), from baseline to week 4 will be tested with a mixed linear model. This model will be adjusted for important demographic variables (i.e., gender) and also baseline clinical parameters where appropriate. All tests will be two-sided (alpha level, 0.05). We will initially test our main hypothesis that the combined treatment induces a greater increase in CPM (and decrease in TSPS) as compared to the control condition. If the effect is significant, we will then test differences between the combined group vs these two interventions alone.

[figure not shown]
In order to understand the time effect of this intervention (using the secondary endpoints added in this model (week1 and follow-up)), we will run a secondary mixed linear model to estimate the rate of change over time by also including an interaction between treatment and time as to detect whether treatment effect changes differently according time. If the interaction is not significant we will then test whether there is a main effect of time that is independent of treatment level (interaction will be then removed from the model). We will adjust this model for important covariates such as age, gender, pain levels (numeric pain scale – NPS), and other baseline clinical outcomes where appropriate. For the secondary clinical variables with a significant effect we will also test whether they moderate the interventions' effects on our mechanistic outcomes, thereby gaining additional mechanistic insights.

To complete our analysis, we will apply a path analysis [1, 2] to the outcome data (CPM and TSPS) to determine if endogenous pain modulation changes (as indexed by CPM and TSPS) associated with the combined intervention (tDCS and AE) is related to direct effects versus indirect effects through improvements in secondary outcomes. We propose that a direct effect of tDCS and AE on the endogenous pain inhibitory system can be inferred if the treatment effect cannot be explained by changes in psychological or functional outcomes.

[figure not shown]

[figure not shown]
Detailed Protocol 23

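### CPM and TSPS share the primary aim and main hypothesis, but TSPS has no stated role, the gate to the single-intervention comparisons names no endpoint, and the sizing covers one test

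*Combined protocol and SAP*

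**What the plan says.** Section VIII, Planned Analysis, describes the primary test: "The change in the primary efficacy endpoint, CPM (and also TSPS), from baseline to week 4 will be tested with a mixed linear model". The main hypothesis there is that the combined treatment raises CPM, and (in brackets) lowers TSPS, more than control does. Every test is two-sided at 0.05. If that effect is significant, the combined group is then compared with each intervention alone. The sentence does not say whether the effect meant is on CPM, on TSPS, on either or on both.

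Elsewhere the two markers stand side by side. Section II, Aim 1, which carries the primary-outcome label, concerns the "endogenous pain regulatory system assessed by CPM and central sensitization as assessed by TSPS" and predicts a "greater decrease in SPS and increase in CPM responses". Section I states that the mechanism will be studied "via two important markers of chronic pain, conditioning pain modulation (CPM) and slow temporal summation (STS", and Sub-aim 3 calls the pair "the two main targets tested in this study".

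The Sample Size Calculation in section VIII proceeds by "using the t-test calculation for the difference between two independent means (to test for the main hypothesis", with an effect size of 0.90, 5% type I error and 20% dropout. It "determined that we need a total of 116 participants (29 in each group) to achieve 85% power". It does not say whether 0.90 refers to CPM or to TSPS.

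**The concern.** The main hypothesis contains two effects, and the plan does not say how a split result would be read. A split is foreseeable: Aim 1 itself expects exercise to act more on the structures indexed by summation and tDCS more on those indexed by CPM.

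Three success rules fit the text: CPM decides, either marker suffices, or both are needed. They have different error rates and different power, and only the first matches the stated 5% and 85%. The same gap affects the gate. If CPM fails and TSPS succeeds, or the reverse, the plan does not say whether the comparisons with the single interventions go ahead. Left open, both matters can be settled after the results are known.

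**Working it through.** **Inputs.** From section VIII: effect size 0.90, two-sided alpha 0.05, power 85%, dropout 20%, 29 per group, 116 in total. Assumed here: the correlation between the endpoints (0 to 0.7, oriented so that benefit is positive on both), an effect of 0.90 on TSPS as well as CPM, and the step-2 effects shown below. Simulations use two-sample t-tests, the plan's own sizing method, with four arms and two endpoints.

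**1. The plan's sample size.** The normal approximation gives n = 2(1.960 + 1.036)² / 0.90² = 22.2, so 23 per group. Then 23 / 0.8 = 28.75, so 29, and 29 × 4 = 116. The exact t-test gives 23.17, and 23.17 / 0.8 = 28.96, again 29. The figure reproduces as one comparison, on one effect size, at full alpha.

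**2. One pre-named endpoint decides.** The noncentrality is 0.90 × √(n/2).
- n = 23: 3.05 on 44 df, power 84.7%.
- n = 29: 3.43 on 56 df, power 92.0%.
- Type I error for this contrast: 5%.

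**3. A win on either endpoint counts (no effect on either).** At correlation 0, 1 − 0.95² = 9.75% counting both directions. In the favourable direction only it is 1 − 0.975² = 4.9%, against a nominal 2.5%. Simulation gives about 9.5%, 9.1% and 8.3-8.4% at correlations 0.3, 0.5 and 0.7. The favourable-direction rate stays between about 4% and 5%.

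**4. Both must win (0.90 on each).** At correlation 0, joint power is 0.847² = 72% with 23 completers and 0.920² = 85% with 29.

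| Correlation | 0 | 0.3 | 0.5 | 0.7 |
|---|---|---|---|---|
| 23 per arm | 71.6% | 73.6% | 75.5% | 77.2% |
| 29 per arm | 84.8% | 85.6% | 86.4% | 87.5% |

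These are unadjusted t-tests. The planned covariate adjustment could raise them: with 23 completers, joint power is 77-82% if the covariates correlate 0.3 with the outcome, and 87-89% at 0.5.

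**5. The gated comparisons on CPM.**
- Combination equal to both single interventions, all 0.90 above control: at least one gated comparison is significant in about 7% of trials counting both directions (6.8% with 23 per arm, about 7.5% with 29). Counting only false superiority of the combination, it is about 4.5%.
- Combination 0.90 and each single intervention 0.45 above control, 23 per arm: at least one gated comparison succeeds in about 44% of trials, and both succeed in about 17%.

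**The case against.** The strongest reply is that the plan does name its primary endpoint. The analysis section uses the singular, names CPM, and brackets TSPS each time. On that reading the first contrast has its 5% and about 85%, and nothing is inflated. No sentence says that a win on either marker is enough. The hypotheses join the markers with 'and', which fits a both-required rule at least as well, and that rule inflates nothing. The wording in section I and Sub-aim 3 is background and correlational, and assigns no testing status. In a mechanistic trial, testing each marker at 0.05 is a recognised convention.

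Much of this stands. A reader might infer that the plan runs at a 9.75% error rate, or that 116 is miscalculated. The documents support neither: the first depends on a success rule the plan does not state, and the sample size reproduces. A reader might also take about 7% as the rate of false superiority claims at step 2. It is not, because it includes trials in which the combination looks significantly worse; the superiority-only figure is about 4.5%.

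The reply does not settle what TSPS is for. A bracket is not a testing order. Aim 1 gives the primary label to both markers, and the gate sentence follows a hypothesis that contains two effects. A both-required reading would also leave the stated 85% unsupported for that joint test.

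**Conclusion.** The concern holds as a gap in the decision rule, and it should be fixed. The readable text leans to CPM without ranking the endpoints, gives TSPS no stated role, and leaves the gate's endpoint unnamed. The size of the consequence depends on the reading:

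- CPM alone decides: no loss on the first contrast.
- Either counts: two-sided type I error of about 8.3-9.75%.
- Both required: joint power of 72-77% with 23 completers per arm and unadjusted tests, or 85-87% with 29.

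These figures rest on the assumed correlations and on an assumed 0.90 for TSPS. Confidence is medium, because the figures beside the sizing and analysis text, and appendix 2, were not readable and might contain a rule.

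**What to change.** Following the analysis section's own lean:

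1. Name CPM, combined versus control, as the single primary test at two-sided 0.05.
2. Test TSPS, combined versus control, confirmatorily only if CPM is significant.
3. State that the CPM result opens the comparisons with the single interventions.
4. For those two comparisons, either label them secondary with no confirmatory claim, or place them in the same sequence as TSPS with both required. The sponsor chooses the option and the order.

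If the sponsor instead means that both endpoints must win, keep 0.05 for each and restate the joint power with its assumptions on effect size, correlation, dropout and covariates.

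The cost is a few sentences and no extra patients, and the first CPM contrast keeps about 85%. The price is that later claims depend on earlier ones. With 23 completers per arm and 0.90 on each endpoint, a TSPS claim after CPM has about 72-77% power, not 85%. At an assumed advantage of 0.45 over each single intervention, a both-required claim passes in about 17% of trials if placed straight after CPM, or 14-16% if placed after TSPS, against about 44% for at least one comparison as written. Placing it before TSPS lowers the TSPS claim to 14-16% in that scenario. Labelling the comparisons secondary keeps the 44%, without a confirmatory claim.

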**Visits 0 and 1 may be completed in the same day or broken up into two separate visits as the subject prefers*

Daily pain reports will be collected for the two weeks between V1 and V2.

VISITS 1.1 – 1.3: Subjects will be randomized during visit 1.1. The two groups will participate in a different conditioning exercise program for two weeks according to their group assignment (see section VI). At visits 1.1, we will conduct assessments of pain, quality of life, TPSP, CPM, TMS and EEG acquisition (we will offer the possibility of splitting this visit into two visits if the subject gets too tired). At visit 1.3, we will conduct assessments of pain and quality of life, TPSP and CPM. In all these visits we will conduct AE adverse effects questionnaires.

VISITS 2, 11, 17: assessments of pain (except visit 2), quality of life (except visit 2), TSPS, CPM, TMS and EEG acquisition. At the same visit, tDCS and AE will be performed. Also, tDCS and AE adverse effects questionnaire.

VISITS 6 and 14: tDCS, AE, tDCS and AE adverse effects questionnaire, CPM, TSPS, assessments of Pain

[figure not shown]
VISITS 3, 5, 8, 10: tDCS only and tDCS adverse effect questionnaire. The subjects will have the option of choosing to do the visits remotely home-based tDCS (Soterix Medical 1X1 tDCS mini-CT stimulator device), in order to decrease the burn of daily visits at our site.

[figure not shown]
VISITS: 4, 7, 9, 12, 13, 15, 16: tDCS, AE and tDCS and AE adverse effects questionnaire.

VISIT: 18: Pain and quality of life assessments, TMS, EEG, CPM, TSPS.

[figure not shown]
Replacement of missed sessions (though all the effort will be made to avoid missing sessions) will be allowed to up to 20% of missed sessions (up to 4 total visits) according to the treatment schedule. Follow-up and assessments will be encouraged even if more than 20% of missed sessions given data will be analyzed as ITT (though we expect this to be low). We will allow the following visit windows:

- *between visit 1 and 1.1: 2 weeks*
- *between visits during the conditioning period (from visit 1.1 to 1.3): 2 weekdays*
- *between visit 1.3 and visit 2: up to 1 week*
- *between visit 17 and visit 18: up to 2 weeks (before or after the final follow-up, meaning visit 18 could happen 2.5 months to 3.5 months from visit 17)*
- *between Visit 2 and Visit 17: up to 6 weeks*

[figure not shown]

Detailed Protocol 16

Detailed Protocol 17

VII. DESCRIPTION OF ASSESSMENTS

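### The only readable model of time does not name collected visits 11 and 14 and drops a non-significant arm-by-time term, so it locates the onset of effect more coarsely than the data allow

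*Combined protocol and SAP*

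**What the plan says.** Section II, Aim 3, sets a question about time: "Assess the number of sessions needed to induce significant changes in markers of endogenous pain inhibitory system". It also covers "cortical changes (as indexed by paired pulse TMS and EEG". Its hypothesis compares arms: the combined group "will have a greater number of subjects with target engagement (change of at least 30% as compared to baseline) of pain and cortical marker".

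The visit description collects more time points than the analysis names:

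- "VISITS 2, 11, 17: assessments of pain (except visit 2), quality of life (except visit 2), TSPS, CPM, TMS and EEG acquisition"
- "VISITS 6 and 14: tDCS, AE, tDCS and AE adverse effects questionnaire, CPM, TSPS, assessments of Pain"
- CPM and TSPS are also measured at visits 1.1, 1.3 and 18. TMS and EEG are also recorded at visits 1.1 and 18.

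Section VIII, Planned Analysis, has two readable models of the markers over time. The primary one tests the change from baseline to week 4. The secondary one is introduced with "In order to understand the time effect of this intervention (using the secondary endpoints added in this model (week1 and follow-up" and is meant "to estimate the rate of change over time by also including an interaction between treatment and time". If that interaction is not significant, a main effect of time is tested instead and the "interaction will be then removed from the model". The text does not say whether time enters as a straight line or as separate visits.

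**The concern.** The added time points are given as a closed pair, not as examples. Between the early point and week 4 the model then contains no CPM or TSPS value, although participants are tested twice in that interval. A question about how many sessions are needed depends on exactly that interval.

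The removal rule adds a second problem. A non-significant interaction does not show that the arms share a time course. Once the term is gone, the fitted model has one time course for all arms, while the aim that most needs a time course is about how the combined arm differs from the others.

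What is at stake is the mechanistic reading of timing: data already collected would not be used to narrow it.

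**Working it through.** **Session count.** tDCS is given at visits 2, 11 and 17; 6 and 14; 3, 5, 8 and 10; and 4, 7, 9, 12, 13, 15 and 16. That is every visit from 2 to 17, or 3 + 2 + 4 + 7 = 16 sessions, which matches the 16 stated in Section II. Visits 2, 6, 11, 14 and 17 are therefore sessions 1, 5, 10, 13 and 16.

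**Method.** Take an effect that starts at session *s* and persists. Its expected pattern at the modelled visits depends only on which of them come after *s*. Onsets with the same pattern cannot be told apart at any sample size. Follow-up does not help, because every persistent effect is present there.

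**CPM and TSPS, if *week1* is visit 6 and week 4 is visit 17:**

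| Markers relative to that day's session | Named points only | With visits 11 and 14 |
|---|---|---|
| After | 6–16 (11 sessions) | 6–10, 11–13, 14–16 (5, 3, 3) |
| Before | 5–15 (11 sessions) | 5–9, 10–12, 13–15 (5, 3, 3) |

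The width is 16 − 5 = 11 or 15 − 4 = 11, so the unstated order does not change it.

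**If *week1* is the conditioning week.** The only readable use of that label elsewhere is the exercise conditioning schedule, before any tDCS. Visit 17 is then the only on-treatment point in the model, and the block is 16 sessions (markers after) or 15 (markers before).

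**TMS and EEG.** No readable analysis names them. They are not recorded at visits 6 or 14, and visit 11 is their only assessment between visits 2 and 17. From visit 2 to visit 17 the block is 15 sessions; visit 11 splits it into 9 and 6. Visit 14 cannot help here.

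**What the extra visits can and cannot do.** The sample size section gives d = 0.90, 85% power, two-sided 0.05 and 20% dropout. By the normal formula, 2(1.960 + 1.036)²/0.90² = 22.2, so 23 per arm; 23/0.8 = 28.75, so 29 per arm and 116 in total, as stated. With 23 completers per arm, combined versus control, assume that the effect accrues evenly, so that *k* sessions contribute 0.90 × *k*/16:

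| Step | *k* | d | Power, same SD for every change | Power, correlation 0.8 between treatment visits and 0.5 with baseline |
|---|---|---|---|---|
| Visit 14 to 17 | 3 | 0.169 | 9% | 14% |
| Visit 6 to 11 | 5 | 0.281 | 15% | 31% |
| Visit 6 to 17 | 11 | 0.619 | 54% | 90% |

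The last column divides d by √(0.4/1.0) = 0.632. If instead the whole effect arises after visit 14, the first step has 85% power under the equal-SD assumption. The added visits locate an abrupt onset well and a gradual one poorly.

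**How often the interaction would be removed.** Assume week-4 effects of 0, 0.45, 0.45 and 0.90 that persist to follow-up, 23 per arm, baseline as one of the outcome times, and compound symmetry.

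- Categorical time (9 and 264 df), d on the change SD: 14% to 32% across three onset profiles.
- Categorical time, d on the post-treatment SD: about 0% to 50% for correlations from 0.8 to 0.3.
- Linear time at weeks 0, 1, 4 and 17, d on the change SD: about 29% to 78% by simulation. The mean week is 5.5, so follow-up carries 11.5²/185 = 71% of the slope's leverage.

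If baseline is a covariate instead, an effect fully present by week 1 and constant afterwards has no post-baseline interaction, and a 5% test rightly drops the term in 95% of trials. The range is roughly 0% to 78% and depends on model form, so it is not a usable size.

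**The case against.** **The plan may already cover this.** Several figures in and after Section VIII are not shown, and the secondary model is not labelled as the Aim 3 analysis. This stands. A reader might infer that the trial has no analysis for Aim 3 or cannot address it; the documents do not support that. They support only that no readable analysis gives the number of sessions or the 30% proportion, and that the printed time model omits visits 11 and 14.

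**The figure of 11 of 16 rests on an inference.** No readable text ties *week1* to visit 6 or week 4 to visit 17. This also stands, so the figure is conditional. The other readable meaning of the label widens the block.

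**The removal rule is harmless.** It serves a test of the main effect of time; the plan does not say that the fuller model goes unreported, and a 30% responder comparison does not depend on it. This stands in part. A reader might infer that a real interaction would be lost in some stated share of trials, but the calculation gives no dependable share. What remains is that the stated rule ends with a single pooled time course.

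**Using more visits buys little.** Under gradual accrual, power for adjacent steps is low. That is true and should be stated in the SAP. It is no reason to leave out measurements already taken, because without them the 11-session block cannot be divided at all.

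**Conclusion.** The point holds on the readable text as a cheap improvement to a secondary analysis, between optional and recommended. The printed time model adds only *week1* and follow-up to baseline and week 4. With *week1* as visit 6 and week 4 as visit 17, persistent onsets across 11 of 16 tDCS sessions are indistinguishable; visits 11 and 14 cut that to 5, 3 and 3. If *week1* is the conditioning week, the block is 15 or 16 sessions. These counts assume that the listed time points are complete and that effects persist once they start; they need no assumption about effect size or variance.

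The rule that drops the interaction is a weaker way to describe arm-specific timing, but no frequency can be attached to it. A reader might also infer that the main result is compromised. It is not: the week-4 contrast is a separate model, and the 116 participants do not depend on the time model.

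**What to change.** In the secondary time model:

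1. Use every collected post-randomisation visit as categorical time: 1.3, 2, 6, 11, 14, 17 and 18 for CPM and TSPS; 2, 11, 17 and 18 for TMS and EEG if they are modelled. Visits 1.3 and 2 belong in the model because the arms already exercise differently during conditioning; without them, conditioning effects merge with those of the first tDCS sessions.
2. Keep arm-by-visit whatever its p-value, and report the arm contrast with its interval at each visit.
3. Use the visit 1.1 marker value as the baseline covariate, after confirming that it is measured before randomisation and the first exercise session. Both fall at visit 1.1, and the visit description does not give the order.
4. State which visit *week1* is, and whether markers precede that day's session.
5. If the 30% engagement proportion is reported by visit, define it for zero or negative baselines. Section VII defines CPM and TSPS as difference scores, and Section I cites pain facilitation during CPM in 41.7% of patients, so a percentage change can be undefined or unstable.
6. Report onset as a window of sessions, and say that gradual onset will be poorly located.
7. Keep the week-4 contrast as primary.

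If content not shown here already specifies an Aim 3 analysis, cross-refer to it and align the two. The cost is SAP wording and a slightly larger model, with no new visits or data.

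### The secondary time model's target reads as a single slope across treatment and a distant off-treatment follow-up, and its rule for dropping the interaction would then usually discard a real rise-and-fade effect

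*Combined protocol and SAP*

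**What the plan says.** Section VIII (Planned Analysis) sets out two models for CPM and TSPS.

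- **Primary.** The change "from baseline to week 4 will be tested with a mixed linear model".
- **Secondary.** For the time course, the plan states: "we will run a secondary mixed linear model to estimate the rate of change over time". The visits brought in beyond the primary pair are named in the same sentence ("using the secondary endpoints added in this model (week1 and follow-up"). The treatment-by-time term is described as "including an interaction between treatment and time as to detect whether treatment effect changes differently according time".
- **Removal rule.** "If the interaction is not significant we will then test whether there is a main effect of time that is independent of treatment level"; the interaction is then taken out of the model.

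Section II gives the treatment length: "Evaluate the effects of 4 weeks of tDCS coupled with exercise". The visit description places follow-up well after that, "meaning visit 18 could happen 2.5 months to 3.5 months from visit 17". It lists only assessments at visit 18 ("Pain and quality of life assessments, TMS, EEG, CPM, TSPS"), with no stimulation or exercise.

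The visible text does not say whether time is a continuous variable or a visit factor, whether a continuous term may bend when treatment stops, or which contrast at follow-up is of interest.

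**The concern.** A rate of change is a quantity per unit of time, and a model that delivers one usually has a single linear time term. Here that line would join a 4-week treatment phase to an off-treatment gap roughly three to four times as long. An effect that builds to week 4 and then partly fades is not a straight line. The remote follow-up visit would largely fix the slope, and the week-4 visit, where the effect should be largest, would hardly influence it.

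The removal rule adds to this. A non-significant slope difference would be read as no time-varying treatment effect, and the report would move on to a time trend common to all arms. In the visible analysis text this is the only model that uses visit 18 to judge persistence, so the question the model exists to answer could be lost.

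**Working it through.** **The plan's own figure.** The secondary model has no power statement, but the sample size gives the arm size used below. Per arm, n = 2(1.960 + 1.036)²/0.90² = 22.2, so 23. With 20% dropout, 23/0.80 = 28.75, so 29, and 4 × 29 = 116. The protocol's total is reproduced (an exact t calculation gives 24 per arm before dropout).

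**Inputs.** From the documents: baseline, week 1, week 4, follow-up 2.5 to 3.5 months after visit 17, effect size 0.90, two-sided alpha 0.05. At about 4.35 weeks per month, follow-up falls at 4 + 2.5 × 4.35 = 14.9 to 4 + 3.5 × 4.35 = 19.2 weeks, with 17 central. Assumed: one linear time term with free arm intercepts; combined-versus-control differences of 0, 0.3 and 0.9 SD at weeks 0, 1 and 4; a fraction k of the 0.9 retained at follow-up; 23 per arm; compound symmetry with correlation 0.5 (at which the SD of change equals the SD).

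**Leverage.** For times 0, 1, 4, 17 the mean is 5.5 and the squared deviations are 30.25, 20.25, 2.25 and 132.25, summing to 185. Follow-up carries 132.25/185 = 71%; week 4 carries 2.25/185 = 1%. Over 14.9 to 19.2 weeks these are 70-72% and 1-2%.

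**Fitted slope and week-4 difference.** Slope = (−4.5 × 0.3 − 1.5 × 0.9 + 11.5 × 0.9k)/185 = (−2.70 + 10.35k)/185. Fitted week-4 difference = (1.2 + 0.9k)/4 − 1.5 × slope.

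**Power of the slope test.** The standard error of the slope difference is √[(0.5/185) × (2/23)] = 0.0153. Power is from the noncentral t with 44 df.

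| k | slope, SD/week | fitted week-4 difference (true 0.90) | slope/SE | power |
|---|---|---|---|---|
| 0 | −0.015 | 0.32 | −0.95 | 15% |
| 0.25 | −0.001 | 0.36 | −0.04 | 5% |
| 0.5 | +0.013 | 0.39 | 0.87 | 14% |
| 1 | +0.041 | 0.46 | 2.70 | 75% |

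Simulation of the same setting gives 16%, 5%, 14% and 75%. The week-4 change in the same data is significant in about 85% of trials. Over the whole follow-up window the fitted week-4 difference stays between 0.31 and 0.48.

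**Sign.** The slope is zero at k = 2.70/10.35 = 0.26, so it turns negative only below about a quarter retained. At k = 0 the fitted differences at weeks 0, 1, 4 and 17 are 0.38, 0.37, 0.32 and 0.13, all favouring treatment. If the line is forced through zero difference at baseline, the slope at k = 0 is (0.3 + 4 × 0.9)/(1 + 16 + 289) = +0.013 and does not reverse.

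**Sensitivity and alternative.** With a linear build-up instead (0.225 SD at week 1) and 24 per arm, the fitted week-4 difference is 0.30 to 0.44. Slope power is 14%, 5%, 17% and 82% for the same k, against 87%, 80%, 79% and 93% for the 3-df arm-by-visit test with visit as a factor. At k = 0, correlations from 0.3 to 0.7 give 11-20% for the slope and 73-98% for the factor test. In this profile the sign threshold is 20-25% retained, 27-33% if weeks 2 and 3 also enter, and 49-52% if baseline is a covariate and not an outcome.

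**The case against.** The strongest reply is that the plan never says time is linear. A mixed linear model is linear in its parameters, and visit as a factor is one of its forms. Calling week 1 and follow-up endpoints, and testing a main effect of time, fits a factor too. With a factor there is no flattening and no sign change. Figures near this text are not shown, so a fuller specification cannot be excluded. This stands: a reader might infer that the protocol prescribes a straight line, and the documents do not establish that. It does not remove the need to act. If a factor is meant, a rate is the wrong description; if a slope is meant, it suits the schedule badly; left open, the choice can be made after the data are seen.

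A reader might also infer that the model would show a harmful or wrong-signed effect. That is not supported. A negative slope needs most of the effect to be lost, depends on how baseline enters, and describes a fading benefit. At complete fade the point estimate is negative in about 83% of trials, but significantly so in only about 15%.

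The low slope leverage of week 4 does not mean the visit is ignored. It still informs the fitted level, with a total hat value of 0.25 + 0.01 = 0.26. The 85% for the week-4 change largely restates the design assumption. The power figures are for one pair of arms, while the trial has four. These points limit how far the exact percentages carry, but not the pattern.

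Finally, Aim 3 looks separately at the on-treatment course, and CPM and TSPS are also measured at visits 6, 11 and 14. That does not cover persistence to visit 18.

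**Conclusion.** The point holds in a conditional form and should be corrected. The stated target, read naturally as one slope, does not suit a schedule with 4 weeks on treatment and a single visit about 3 months later. Under that reading and the assumptions listed, a 0.9 SD week-4 difference is fitted as about 0.3 to 0.5 SD whatever is retained. The slope test is significant in about 5-16% of trials when half or less is retained, and in about 75% when all is. The removal rule would then usually delete a real time-varying effect.

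The build-up profile, retained fraction, correlation, week-17 timing and free arm intercepts are assumptions, not figures in the plan. A reader might infer that the main result is at risk. It is not: the baseline-to-week-4 contrast is a separate model and comes first. The weakness is confined to the time-course and persistence analysis, which makes this a recommended change and not a critical one.

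**What to change.** In the secondary model, replace the rate-of-change target with visit as a categorical factor and arm-by-visit terms. Report the arm contrasts at week 1, week 4 and visit 18, each with a 95% CI, whether or not the overall interaction is significant, and delete the rule that removes the interaction. If a slope is wanted, specify a piecewise model with a knot at visit 17, so that on-treatment change and off-treatment change are estimated separately.

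The cost is a sentence or two and a few degrees of freedom: with four arms and four visits, 3 × 3 = 9 interaction parameters instead of 3, and three time parameters instead of one. No new data are needed.
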